3.4.3 Strategies to improve protocol adherence

The study principal investigators and site principal investigators will be responsible for education about the trial and training clinicians and research staff. Trial interventions will utilize local standardized CRRT order sets.

3.4.4 Cointerventions

Additional aspects of CRRT, including timing, catheter insertion site, selection of clearance mode (e.g., CVVH, CVVHD, CVVHDF), anticoagulation strategy, and net ultrafiltration rate (e.g., total fluid removal rate) will be independent of the allocated intervention and based on the principles of standard best practices and at the discretion of the responsible clinical team.[31] These aspects of the delivery of CRRT will be recorded and reported, as applicable. The management of critical illness, including but not limited to hemodynamic support, ventilatory support, fluid resuscitation and therapy, nutrition, rehabilitation, and medications will also be at the discretion of the responsible clinical team.

3.5 Outcomes

3.5.1 Primary Endpoint

The primary feasibility endpoint is the difference (95% CI) in the total delivered effluent flow rate per patient between those in the lower and standard CRRT dose-intensity groups. The WISDOM pilot trial will target the detection of a minimum difference of 10

mL/kg/hr in average delivered dose-intensity between the groups. This will be an important proof-of-concept endpoint to inform the feasibility of a larger multi-centre trial.

3.5.2 Secondary Endpoints

The secondary feasibility endpoints are:

- i) Ability to enroll an average of 2 patients per site per month. We believe a target of 2 per month is feasible across sites in Alberta given the number of patients starting CRRT per month (~32 new CRRT initiations per month) and accrual at sites during the STARRT-AKI trial.
- ii) The ability to enroll >50% of fully eligible patients.
- iii) Time from eligibility (e.g., starting RRT) to randomization with a target of >75% of eligible patients within 12 hours.
- iv) Protocol adherence for allocated CRRT dose-intensity. We believe a target in-range dose-intensity of >80% to be adequate.
- v) Ability to capture delivered CRRT dose-intensity measures. This is a process measure of trial implementation and fidelity. We believe a target of electronic capturing >95% of daily time-averaged CRRT dose-intensity data to be adequate. This will enable an assessment of difference in CRRT dose-intensity between groups.
- vi) Ability to capture patient and kidney endpoints at 90-days from randomization. We believe a target of >95% ascertainment to be adequate.

3.5.3 Biochemical Endpoints

The biochemical endpoints will assess the tolerability of the intervention and are:

- i) daily serum sodium, bicarbonate, base excess, strong ion difference (SID) and pH while receiving CRRT and number of (%) days without severe acidemia (pH <7.25).
- ii) daily serum magnesium, potassium, and phosphate while receiving CRRT and number of (%) days without hyperkalemia (K^+ >5.5 mmol/L).
- iii) daily serum urea while receiving CRRT and number of (%) days without serum urea >35 mmol/L.

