3.3.1 Inclusion Criteria

Eligible patients will be admitted to an intensive care unit and fulfill the following inclusion criteria:

- i) age \geq 18 years
- ii) patient weight \geq 55 kg
- iii) plan to initiate CRRT or within 24 hours of having started CRRT for AKI
- iv) expected to survive and receive CRRT for a duration of \geq 48 hours
- v) able to provide informed consent or have an authorized representative provide consent after being informed of the details and risks of the trial unless a deferred consent process is approved by the local Research Ethics Board (REB).

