3.5.4 Process of Care Endpoints

The process of care measures will assess the tolerability of the intervention and are:

- i) The lowest and highest CRRT dose-intensity delivered for any given hour following randomization.
- ii) The proportion of hours of CRRT when the dose-intensity is in the target range following randomization.
- iii) The total treatment time/day while receiving CRRT following randomization. This will be defined as time on treatment divided by 24-hours.
- iv) The total number of hemofilter/circuit replacements during CRRT following randomization.

- v) The total volume of replacement/dialysate fluid used per day and overall following randomization.
- vi) The total number and cumulative doses of supplemental electrolytes (Mg⁺, K⁺, PO₄⁻, HCO₃⁻), protein and vitamins administered while receiving CRRT following randomization.
- vii) The modified daily bedside (nursing) activity score, as a measure of nursing bedside workload, while receiving CRRT following randomization.
- viii) The mean daily net ultrafiltration (UF_{NET}) delivery while receiving CRRT following randomization.

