3.5.5 Safety

An adverse event (AE) is any untoward medical occurrence in a patient enrolled in the trial which does not necessarily have a causal relationship with the intervention. A serious adverse event (SAE) is defined as any untoward medical occurrence that results in death, is life-threatening, requires hospitalization (overnight or longer), causes prolongation of existing hospitalization, results in persistent or significant disability or incapacity; results in congenital anomaly or birth defect; other medically important event (is not immediately life-threatening or results in death or hospitalization but may jeopardize the subject or require intervention to prevent one of the above outcomes). Due to this trial being performed in critically ill patients, AEs and SAEs are expected to occur frequently. As such, AE and SAE reporting will follow recommendations set out for trials in this population by Cook and colleagues.[32] This includes a predefined list of AEs that will be considered potentially trial-related AEs and require reporting in the REDCap database. SAEs will be graded based on Common Terminology Criteria for Adverse Events (CTCAE) (grade 1-5) and assigned causality with the intervention (definite, probable, possible or unlikely related).[33] Information related to the trial-related SAEs will be captured on a dedicated form, shared with the study sponsor and submitted to the REB, as applicable (See the Manual of Procedures (MOP) for details of the predefined AEs and recording and reporting requirements for trial-related AEs and SAEs).

Table. Summary of predefined adverse events that will be considered potentially trial-related.

Adverse Event	Definition
Serum K⁺	<3.0 or >6.0 mmol/L
Serum Mg⁺	<0.5 or >1.5 mmol/L
Serum PO₄⁺	<0.5 or >2.5 mmol/L
Serum Urea	>35 mmol (24 hour after randomization)
Serum pH	<7.20 or >7.60 mmol/L
Serum HCO₃	<10 or >35 mmol/L
Serum Ionized Ca⁺	<0.80 or >1.50 mmol/L

Generalized Seizures	Occurrence of a generalized seizure
Arrhythmias	New atrial fibrillation or occurrence of ventricular tachycardia or fibrillation (As defined in STARRT-AKI)

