5. METHODS: ANALYSIS

5.1 Proposed analyses

Baseline characteristics will be summarized with descriptive statistics. The primary feasibility endpoint, the difference in mean (SD) CRRT dose-intensity between groups, will be reported as difference in means (with 95% confidence intervals [CI]). For secondary feasibility, physiological and biochemical, and process of care endpoints, all

continuous variables will describe the number of non-missing values [n], means, medians, standard deviation [SD], interquartile ranges, whereas all categorical variables, will describe frequency counts and percentages, as appropriate. Between group differences will be assessed using Chi-square or Fisher's exact tests for dichotomous outcomes and student t-tests or non-parametric methods for continuous outcomes, as appropriate. A mixed linear regression for repeated measures will be performed, adjusted for baseline variables and CRRT duration, to evaluate dose-intensity differences by allocated group. Safety endpoints will describe and compare the occurrence of AE, SAE and SAE leading to intervention discontinuation overall and by allocated CRRT dose-intensity.

The WISDOM pilot trial is not designed and will be inadequately powered to detect important differences in clinical outcomes and effect estimates may be inaccurate with large confidence intervals.[34]

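### The biochemical tolerability endpoints have no post-randomization start, and the protocol's baseline-adjusted model is not applied to them

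*Protocol*

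**What the plan says.** Section 3.5.3 introduces its list with "The biochemical endpoints will assess the tolerability of the intervention and are". The three items cover acid-base and sodium, electrolytes, and urea. Each combines daily values with a count or percentage of days free of a threshold breach, and each is bounded only by being on CRRT: "daily serum magnesium, potassium, and phosphate while receiving CRRT and number of (%) days without hyperkalemia" for the electrolytes and "daily serum urea while receiving CRRT and number of (%) days without serum urea >35 mmol/L" for urea. None has a start point, and the Summary is equally open.

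Neighbouring definitions do set a clock. All eight process measures in section 3.5.4 are limited to time after randomization, for example "The total treatment time/day while receiving CRRT following randomization". In section 3.5.5 the urea adverse event reads ">35 mmol (24 hour after randomization". The persistence criteria in section 3.4.2 also count 24 hours from randomization.

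On timing, section 3.3.1 admits patients at "plan to initiate CRRT or within 24 hours of having started CRRT for AKI". Section 3.4.1 gives both arms the standard dose-intensity for 12 to 24 hours, counted from CRRT start and not from randomization.

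For between-group comparisons, section 5.1 names Chi-square or Fisher's exact tests and "student t-tests or non-parametric methods for continuous outcomes, as appropriate". Its one baseline-adjusted model, a mixed linear regression for repeated measures, is "adjusted for baseline variables and CRRT duration, to evaluate dose-intensity differences by allocated group".

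**The concern.** Values taken before randomization cannot reflect the allocated dose. Counted as outcome, they add a part that is the same in expectation in both arms and so pull the arms together. For a tolerability endpoint that pull could falsely reassure about the lower dose-intensity. Used as a covariate, the same values would explain part of the between-patient variation instead.

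These endpoints are the pilot's main biochemical evidence on whether the lower dose-intensity controls urea, acid-base status and potassium, ahead of a trial with a mortality non-inferiority outcome. The protocol already contains a suitable repeated-measures model but assigns it only to dose-intensity.

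**Working it through.** **The plan's own figures.** The protocol gives no power or precision figure for the biochemical endpoints. The two figures used below reproduce:
- Mean CRRT course (section 2.3): 2,790 / 518 = 5.39, stated as 5.4 days.
- Sample size (section 3.6), two-sided alpha assumed: n per arm = 2 × (1.960 + 1.282)² × 15² / 10² = 47.3, rounded up to 48, so 96 in total, inflated to 100 (50 per arm).

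**Step 1: dilution from an open window.** Let T be days on CRRT and p the days of CRRT before randomization. With no effect before randomization, a per-patient mean or percentage of days keeps the fraction 1 − p/T of the contrast. From section 3.3.1, p runs from 0 (randomized before CRRT starts) to 1 day.

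| T (days) | p = 0 | p = 6 h | p = 12 h | p = 24 h |
|---|---|---|---|---|
| 2 | 100% | 87.5% | 75% | 50% |
| 3 | 100% | 91.7% | 83.3% | 66.7% |
| 5.4 | 100% | 95.4% | 90.7% | 81.5% |
| 10 | 100% | 97.5% | 95% | 90% |

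At T = 5.4 the loss is 0% to 18.5%, and 0.5/5.4 = 9.3% at 12 hours. T = 2 is the shortest course that inclusion criterion iv expects.

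**Step 2: what that does to power.** With 50 per arm, the effect detectable with 80% power is (1.960 + 0.842) × √(2/50) = 0.56 SD. With the SD held fixed:
- contrast kept 90.7%: power 72%
- contrast kept 81.5%: power 63%
- contrast kept 50%: power 29%

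These rows treat every patient as having the same p and T, so they are bounds for illustration and not forecasts.

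**Step 3: precision from the baseline value.** For a continuous value adjusted for its own baseline with correlation ρ, the residual variance is multiplied by 1 − ρ². The documents give no ρ, so a range is shown for the same 0.56 SD effect in a correct window.

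| Assumed ρ | Variance factor | Reduction | Power |
|---|---|---|---|
| none used | 1.00 | 0% | 80% |
| 0.3 | 0.91 | 9% | 84% |
| 0.5 | 0.75 | 25% | 90% |
| 0.7 | 0.51 | 49% | 97.5% |

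The last row follows from 1 − 0.7² = 0.51: the variance factor is 0.51 and the reduction 49%.

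**Step 4: what the randomization limit leaves in place.** The common run-in counts from CRRT start. A patient randomized before CRRT starts still has 12 to 24 hours of common standard dose after randomization, which is 9.3% to 18.5% of a 5.4-day course. A patient randomized at hour 24 has none. The limit therefore removes the pre-randomization part and not all of the common-treatment part.

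**The case against.** The strongest reply is that the protocol nowhere says pre-randomization values count. Section 3.5.3 speaks of tolerability of the intervention, and no allocated intervention exists before randomization. The contrast with section 3.5.4 is not decisive either: the Summary's process item on supplements uses the bare on-CRRT wording for an endpoint that section 3.5.4 limits to time after randomization. This stands. Inclusion is the literal reading of open wording, not a stated rule.

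A reader might also infer that 9% to 19% of every patient's outcome time precedes randomization. The documents do not support that. That share belongs to the 12 to 24 hour run-in. Pre-randomization CRRT is zero for some patients, and if the section 3.5.2 target (more than 75% randomized within 12 hours) is met, the loss for most is at most about 9% at T = 5.4.

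A reader might infer that the unadjusted tests are biased because chance baseline imbalance is credited to dose. That does not hold. The imbalance has a standard error of √(2/50) = 0.2 SD, but under randomization the test's standard error already allows for it. The loss is precision only.

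Finally, section 5.1 says tests will be used as appropriate, and section 6.1 foresees a detailed statistical analysis plan that could add covariates. This makes the adjustment part the weaker half: a cheap improvement, not an omission. It does not reach the window, which is an endpoint definition the protocol itself states.

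**Conclusion.** The point holds as an unclear endpoint window plus an avoidable loss of precision. Read literally, section 3.5.3 counts up to 24 hours of pre-randomization CRRT as outcome. This costs 0% to 18.5% of a per-patient contrast at 5.4 CRRT days, about 9% at 12 hours, and up to 50% for a 2-day course. The unadjusted comparisons in section 5.1 are valid but less precise than the protocol's own mixed model would be: adjusted variance would be 0.91, 0.75 or 0.51 of the unadjusted at an assumed correlation of 0.3, 0.5 or 0.7.

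Assumptions: no dose effect before randomization; 5.4 days comes from all Alberta CRRT patients, of whom an estimated 77% met AKI criteria, not from trial patients; the correlations are not in the documents; and the variance gain applies to continuous daily values, not to the counts or percentages of days without a breach. These are secondary endpoints of a pilot with no power claim, so the primary endpoint and the sample size are unaffected.

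**What to change.** 1. In section 3.5.3 and the Summary, add *following randomization* to all three biochemical items, with the same start rule in both arms.
2. As a sensitivity analysis, exclude the common standard-dose run-in, again by one rule applied alike to both arms.
3. In section 5.1, extend the existing repeated-measures mixed model to the daily laboratory values, adjusting each for the last value of the same analyte before randomization (urea for urea, pH for pH). Do not use a later value as baseline. The run-in can end at hour 12, so a value taken near hour 24 after CRRT start may already reflect the allocated dose, and adjusting for it could remove part of the effect.

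Cost: a few words in two places, one clause in section 5.1 and a little more analysis work, using laboratory values that are routinely recorded. No extra patients are needed and no clinical rule changes. The one real downside is that patients whose CRRT ends soon after randomization will contribute few or no outcome days, so their number should be reported by arm.

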3.5.4 Process of Care Endpoints

The process of care measures will assess the tolerability of the intervention and are:

- i) The lowest and highest CRRT dose-intensity delivered for any given hour following randomization.
- ii) The proportion of hours of CRRT when the dose-intensity is in the target range following randomization.
- iii) The total treatment time/day while receiving CRRT following randomization. This will be defined as time on treatment divided by 24-hours.
- iv) The total number of hemofilter/circuit replacements during CRRT following randomization.

- v) The total volume of replacement/dialysate fluid used per day and overall following randomization.
- vi) The total number and cumulative doses of supplemental electrolytes (Mg⁺, K⁺, PO₄⁻, HCO₃⁻), protein and vitamins administered while receiving CRRT following randomization.
- vii) The modified daily bedside (nursing) activity score, as a measure of nursing bedside workload, while receiving CRRT following randomization.
- viii) The mean daily net ultrafiltration (UF_{NET}) delivery while receiving CRRT following randomization.

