3.4 Interventions

3.4.1 Study Interventions

All enrolled patients will receive the standard dose-intensity for a maximum of 24 hours and a minimum of 12 hours from the time CRRT is started (not the time of enrollment and randomization) to ensure initial metabolic and azotemic stabilization.

The *experimental arm* will be lower CRRT dose-intensity, defined by a delivered effluent flow rate of **10-15 mL/kg/hr**. The rationale for this lower dose-intensity is based on the observed lower threshold currently delivered in clinical practice and observational data showing that this threshold is acceptable, tolerated and safe.[26-28] The *control arm* will be guideline-directed standard CRRT dose-intensity, defined by a delivered effluent flow rate of **25-30 mL/kg/hr**. The standard dose-intensity aligns with current practice and by recommendations from international CPGs.[31] The standard of care for CRRT dose-intensity provided in ICUs in Alberta in a recent audit and across participating sites in STARRT-AKI (39 Canadian sites) ranged between 26-30 mL/kg/hr. The dose calculation will utilize measured or estimated actual body weight.

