3.4.2 Criteria for discontinuing or modifying allocated interventions

The duration of the intervention will be until CRRT is discontinued due to any of patient death, transition to intermittent RRT (IRRT) or due to kidney recovery with no further requirement for RRT. Transition to IRRT will align with current best practices and align with local standards of care. This will generally occur following hemodynamic stabilization and weaning of vasoactive support (i.e., SOFA_{CV} score <2). Ultimate decisions about transitions to IRRT will be made by the local attending physicians. If during their ICU admission a patient has their CRRT temporarily interrupted (e.g., diagnostic imaging or other investigations; procedures or operations), once restarted, the CRRT will be prescribed according to their allocated dose-intensity. If a patient has prolonged CRRT interruption (>6 hours) (e.g., operative theatre), CRRT will be temporarily restarted at the standard dose-intensity for 6 hours to ensure a period of stabilization, then transitioned to their allocated CRRT dose-intensity, as applicable.

If patients are perceived by the treating ICU team to require a temporary increase in dose-intensity to augment acid-base/metabolic/azotemic control due to critical illness, the following actions should be followed in hierarchical order:

- i) For patients with persistent hyperkalemia, defined as [K+] > 5.5 mmol/L at 24 hours after randomization, the treating ICU team can lower the potassium [K+] concentration in the replacement/dialysis solutions, as per ICU-specific protocols.

- ii) For patients with persistent metabolic acidosis, defined as pH <7.25 and BE < -10 at 24 hours after randomization, the treating ICU team can add supplementary bicarbonate (HCO₃) either as a continuous infusion or bicarbonate can be added to the replacement/dialysate solutions, as per ICU-specific protocols.
- iii) For patients who are refractory to the above modifications to the prescribed CRRT or those who have persistent azotemia, defined as [urea] >30 mmol/L at 24 hours after randomization, the treating ICU team can adjust the dose-intensity to the upper limit of dose-intensity within the allocation. For example, in those patients allocated to the low dose-intensity group (target 10 mL/kg/hr), adjust the prescribed dose to 15 mL/kg/hr.

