3.6 Sample size calculation and recruitment

For the WISDOM pilot trial, our primary sample size consideration will address the detection of a minimum difference in the delivered dose-intensity of CRRT between the groups. For the WISDOM pilot trial, we are targeting a total sample size of 100 patients (50 patients per group). This is based on the ability to detect a minimum difference of 10 mL/kg/hr in dose-intensity, assuming delivery of 25 mL/kg/hr in the standard dose-intensity group and 15 mL/kg/hr in the lower dose-intensity group, with a conservative standard deviation (SD) of 15, 90% power, and an alpha of 0.05. This would translate into a sample of 96 patients (48 patients per group) that will be inflated to 100 to account for any withdrawal or dropout (See Table below).

Table. Sample Size Calculation Estimates.

Scenario	Difference in Dose Intensity	Standard Deviation	Power	Estimated Sample (Total)
1	10	5.0	0.9	12
2	10	7.5	0.9	24
3	10	10.0	0.9	44
4	10	12.5	0.9	66
5	10	15.0	0.9	96
6 (ATN Trial)	15	6.3*	0.9	18
7 (RENAL Trial)	15	15.3**	0.9	100
* From the ATN trial, based on average standard deviation for both groups of the aggregate total effluent flow rate delivered.[18]				
** From the RENAL trial, based on average standard deviation for both groups of the aggregate total effluent flow rate delivered.[17]				

For the WISDOM pilot trial, the total sample of 100 patients would translate into a target recruitment of 4 patients per week (50% of expected eligible) across 5-10 sites, thereby requiring an estimated 6-10 months to complete, if all sites are active.

We will further explore the practicality of identification of eligible patients, site-specific recruitment, protocol adherence, and data monitoring and ascertainment, that will inform the logistical planning and operations of a larger-scale multi-centre trial.[34]

All patients enrolled in the trial will be admitted to and monitored in an ICU setting. The primary and secondary feasibility endpoints, along with biochemical and process of care endpoints will be captured in local hospital medical records (either paper charts or electronic medical records) and data repositories. Data will be captured electronically where feasible, otherwise, standardized paper case report forms will be used. The expected rate of loss to follow-up will be low for ICU and hospital-specific outcomes

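### In-range dose hours are counted from randomization, but the mandatory standard-dose hours run from CRRT start, so a fully compliant low-arm patient is scored out of range and a control patient is not

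*Protocol*

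**What the plan says.** **When standard dose is mandatory.** Protocol section 3.4.1 has all enrolled patients, in both arms, "receive the standard dose-intensity for a maximum of 24 hours and a minimum of 12 hours from the time CRRT is started", and adds that this clock is not the randomization clock. Under section 3.4.2, after an interruption of more than 6 h, "CRRT will be temporarily restarted at the standard dose-intensity for 6 hours" before the allocated dose resumes. The target ranges are 10-15 mL/kg/hr (low arm) and 25-30 mL/kg/hr (control arm).

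**When patients are randomized.** Section 3.3.1 admits patients for whom CRRT is planned or who started it within the last 24 h. Section 3.5.2 (iii) wants more than 75% randomized within 12 h of eligibility, for which it gives starting RRT as the example.

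**What is measured.** Section 3.5.4 (ii) is "The proportion of hours of CRRT when the dose-intensity is in the target range following randomization", with no exclusion of run-in or restart hours. Section 3.5.2 (iv) sets the adherence target: "We believe a target in-range dose-intensity of >80% to be adequate". It gives no window or denominator. Section 3.5.1 states: "The primary feasibility endpoint is the difference (95% CI) in the total delivered effluent flow rate per patient". Neither it nor section 5.1 says when averaging starts or stops. Section 3.6 sizes the trial to detect 10 mL/kg/hr between the arms, and its planning values are given as "assuming delivery of 25 mL/kg/hr in the standard dose-intensity group and 15 mL/kg/hr in the lower dose-intensity group".

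**The concern.** The in-range measure and the run-in use different clocks. Between randomization and the end of run-in, a low-arm patient treated exactly as required receives a dose above the low-arm range. A control patient on the same dose in the same hours is within range. The 6-h restarts act the same way. The measure therefore penalises one arm for following the protocol.

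This is a stated window that gives a biased result, so it is more than a detail left open. It also sets two feasibility aims against each other: the sooner patients are randomized, which section 3.5.2 (iii) counts as success, the more run-in hours fall into the low arm's denominator.

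At stake is how the pilot's adherence is read and, depending on the window chosen, the dose separation that section 3.5.1 calls proof of concept for the larger trial.

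**Working it through.** **Inputs.** Difference 10 mL/kg/hr, means 25 and 15, SD 15, 90% power, alpha 0.05, 96 patients raised to 100 (section 3.6). Run-in 12 to 24 h (3.4.1). Restart 6 h (3.4.2). Mean CRRT duration 5.4 days = 129.6 h (2.3, an audit of all Alberta CRRT patients, used as a proxy). Expected CRRT of at least 48 h (3.3.1).

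**The plan's own figure.** n per arm = 2 × (1.960 + 1.282)² × 15² / 10² = 47.3, rounded up to 48, so 96 in total. The stated size reproduces (two-sided). Power at 48 per arm is 90.4%.

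**Formulas.** Let r be the mandated standard-dose hours after randomization and T the CRRT hours counted.
- Low-arm in-range ceiling under perfect compliance = 1 − r/T. The control-arm ceiling stays at 100%.
- Expected difference in time-averaged dose = (standard − low) × (1 − r/T).

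**In-range ceiling, low arm.**
- T = 129.6 h: r = 12 gives 1 − 12/129.6 = 90.7%; r = 24 gives 1 − 24/129.6 = 81.5%; r = 24 + 6 gives 1 − 30/129.6 = 76.9%.
- T = 48 h: r = 12 gives 75.0%; r = 24 gives 50.0%.
- The ceiling is 80% or lower when T ≤ r/0.20, that is 60 h for r = 12 and 120 h for r = 24.

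**Difference and power, if the primary average includes these hours (25 vs 15, SD 15).**
- T = 129.6 h, r = 12: 10 × 0.907 = 9.07. Power is 84.2% with 48 per arm (normal approximation) and 85.0% with 50 per arm (t-test).
- T = 129.6 h, r = 24: 10 × 0.815 = 8.15. Power is 75.8% and 76.7% respectively.
- r = 0: 10.0. Power is 90.4% and 91.0% respectively.

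**The same at the range midpoints (27.5 vs 12.5, difference 15).**
- T = 129.6 h: 13.6 (r = 12) and 12.2 (r = 24), both above 10.
- Falling below 10 needs r/T > 1/3. That is 43.2 h at 5.4 days, more than the 24-h maximum run-in, or 16 h at 48 h of CRRT.

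**Sensitivity to duration.** If each patient is averaged separately, using the mean duration understates the effect, because short courses lose a larger share. As an assumed illustration, take half the patients at 2 days and half at 8.8 days (mean 5.4), with r = 24 h. The mean share of hours outside the run-in is (0.500 + 0.886)/2 = 0.693, giving an average ceiling of 69% and a planning difference of 6.9.

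**The case against.** Several points on the other side are fair.

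- **Primary endpoint.** A reader might infer that the run-in necessarily dilutes the primary result below 10. The documents do not support that. Sections 3.5.1 and 5.1 state no window, and section 6.1 foresees a detailed analysis plan that could start averaging after the run-in. Even with run-in hours included, the midpoints keep the difference above 10 at 5.4 days. The power loss also rests on an SD that section 3.6 calls conservative. With a difference of 8.15 and 50 per arm, power is about 90% at SD 12.5 and 98% at SD 10.
- **Adherence target.** The link from section 3.5.4 (ii) to the >80% target in 3.5.2 (iv) is inferred, since the text does not say they are one measure. Section 3.4.2 treats as deviations only dose changes for reasons it has not specified, so mandated hours are not deviations. That sharpens the problem, because the same hours are compliant under 3.4.2 and out of range under 3.5.4 (ii).
- **Worst-case inputs.** The 24-h figures assume randomization by CRRT start and the longest run-in. Randomized at 6 h and switched at 12 h, the ceiling is 1 − 6/123.6 = 95% and the planning difference 9.5. Enrolled patients, selected for expected CRRT of at least 48 h, may also run longer than the audit mean.
- **Go/no-go.** One might read these measures as deciding whether the main trial proceeds. Section 3.5.2 gives targets believed adequate and section 7.9 speaks only of feasibility; there is no explicit progression rule.
- **Safety.** One might want laboratory events moved to the later start as well, since the urea event in section 3.5.5 refers to 24 h after randomization. That wording can mean from 24 h onward, so nothing need be missed. A later start would drop post-randomization events, including those during true low-dose hours in patients switched at 12 h.

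None of this removes the core point: section 3.5.4 (ii) fixes its start at randomization and excludes nothing.

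**Conclusion.** The concern holds for the in-range measure and conditionally for the primary endpoint. As written, section 3.5.4 (ii) is biased against the low arm. Its ceiling under full compliance is 90.7% to 81.5% at 5.4 days for 12 to 24 h counted, 76.9% with 24 h and one restart, and 75% to 50% at 48 h. If the >80% target uses this measure, it can be missed with no departure from the protocol. Run-in alone causes that only when CRRT is short: up to 60 h with 12 h counted, or up to 120 h with 24 h counted.

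If the primary average starts at randomization or CRRT start, the planning difference of 10 can shrink to 9.07 or 8.15 at 5.4 days. Power at SD 15 then falls from about 90% to 84-85% or 76-77%. The planning means are exactly 10 apart, so they leave no margin; the range midpoints do.

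These figures assume time-weighted averaging, run-in delivered at the control-arm rate in both arms, an unchanged SD and the audit mean as a proxy for duration.

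**What to change.** - Compute the in-range proportion and the primary delivered dose-intensity from one time zero used in both arms: 24 h after CRRT start, or randomization if later. A common time is needed because control patients have no dose switch to mark the end of run-in, and 24 h is the protocol's own maximum.
- Leave the 6-h restart periods mandated by section 3.4.2 out of the in-range denominator in both arms.
- State that the >80% target in section 3.5.2 (iv) uses this same definition.
- Keep the from-randomization version as a sensitivity analysis, and report by arm how many patients end CRRT before time zero.
- Keep safety events counted from randomization.

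This changes endpoint wording and no treatment. The cost is that separated hours before 24 h are lost in patients switched earlier, and patients whose CRRT ends before 24 h contribute no value. Those should be few, since entry requires expected CRRT of at least 48 h. The main analysis also becomes conditional on still receiving CRRT at time zero, which is why the sensitivity analysis and the count by arm are needed.
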